8.2. Descriptive Statistics

Describing baseline characteristics as outlined in chapter 4, such as mean (SD) for continuous variables and frequency (percent) for categorical variables, will be presented in tables and -if appropriate – in figures. These data include clinical and anthropometric data, staff time, sleep data, results from questionnaires, sleep diaries and cognitive function test results. In addition, descriptive data from the Withings Actvity-Watch will be presented in tables according to the similar principles. Descriptive statistics will be based on non-imputed data, thus the number of evaluable outcome measurements at the time of primary interest will also be presented. The rate of missing data will be also presented.

8.3 Analysis Populations

• Enrolled Population

The enrolled population will include all individuals who sign the informed consent.

• Intent-to-Treat Population (ITT)

The ITT population will include all patients who are randomized, irrespective of any deviation from the protocol or premature discontinuation. The group assignment will be designated according to initial randomization. The ITT population will serve to enable an analysis of the primary outcome variable (staff time).

• Per protocol analysis population (PPAP) for the primary outcome

All patients finally fulfilling the complete diagnostic pathway (SR och traditional) will constitute the per protocol analysis population for secondary and tertiary outcome analyses.

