- Information from sleep related examinations in the standard pathway will be manually scored by skilled technicians at each center using predefined criteria. Sleep tests in the SR pathway will be pre-scored by artificial intelligence-based algorithms for characterization of sleep and respiration, and the three PSG in the SR pathway will be manually edited only in epochs identified as unclear by the automated scoring process. For patients with indication for PAP, the titration, training and support will be organized applying local routines at each study center. At PAP-follow up, one night sleep evaluation using the SR self-applied polysomnography procedure will be performed in all patients.

- Evaluation of symptoms and cognitive function with standard care questionnaires and the new European Sleep Questionnaire will be performed together with physical activity assessment at baseline, during treatment and at 3 months follow up.
- Estimated number of patients per center to be randomized: N=42 is the targeted number per site

Study Population:

- Main Inclusion Criteria:
 - Referral to the sleep center due to suspected obstructive sleep apnea as the main question for evaluation
 - Male or female aged 18 years and above
 - \circ $\;$ Willing and able to provide written informed consent $\;$
 - Willing and able to comply with the study design schedule and other requirements
 - (e.g. no long-term travel conflicting with the planned visits throughout the study)
- Main exclusion criteria:
 - o Any ongoing treatment for OSA or Central Sleep Apnea
 - Known significant hypercapnic respiratory failure due to chronic obstructive pulmonary disease or other respiratory condition
 - \circ $\;$ Any other clinically determined contraindication for PAP treatment $\;$
 - o Patients participating in any type of weight loss treatment program
 - Unstable congestive heart failure or angina pectoris
 - Any other condition to the judgement of the investigator which potentially may jeopardize the completion of the study according to protocol
 - History of alcohol or drug abuse during the last year, substance use disorder at screening

Study Duration:

The study started in December 2023 with the first patient inclusion and active patient assessments (last patient out) is expected in July 2025.

Figure 1: SR 001 Study Flow Chart

PSG=polysomnography, PG=polygraphy, SR=Sleep Revolution diagnostic pathway, PAP=Positive Airway Pressure treatment

Trial Design

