The WP8 study is designed as a randomized, controlled, parallel-group, multi- center, multicountry, non-inferiority comparative study.

Randomisation

Eligible patients are allocated in a 1:1 ratio between Standard Care procedures and the Sleep Revolution procedure, using a randomization procedure. The randomization was performed in blocks of 4 patients. The randomization allocates the patients to the first diagnostic procedure which is also the basis of the clinical decision making. However, each patient will also be studied with the respective other diagnostic arm (SC or SR).

The randomization process is described in full within the clinical trial protocol. Details of the randomisation including the final random allocation list is held securely and unavailable to unauthorized trial personnel.

4. Study endpoints and analyses

Primary Endpoint:

• Staff time spent for the sleep apnea diagnostic pathway – comparison between Standard Care (SC) and the Sleep Revolution (SR) model in patients with obstructive sleep apnea (OSA). The detailed staff time protocol is provided in Appendix A.

Secondary analyses:

General descriptive analysis of the patient population

• Description of baseline characteristics of all study participants and the two randomised patient groups (Sleep revolution group and standard care group) according to the following variables: anthropometrics, comorbidities, medications, results from questionnaire data like the degree of daytime sleepiness (ESS score) and additional questionnaire data listed below:

Description of completeness and quality of the technical data collected in the study

- Number of sleep recordings with acceptable quality for the Sleep Revolution study arm at least 1, 2 or all three nights of Self applied Somnography (SAS-PSG),
- Number of sufficient nights in the standard care procedure (SC-PSG)

- Number and proportion of sufficient Withing Watch recordings including physical activity and photoplethysmographic data (pulse, sleep apnea assessment)
- Number of sufficiently answered data in the Sleep Revolution APP with regards to
 - o Sleep diary
 - o Symptom assessment
 - Cognitive test battery
 - Lifestyle information
- Number of sufficiently answered data in the European Sleep Questionnaire data,
- Number of sufficiently answered questionnaires in the Sleep Revolution platform

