$n = f(\alpha_s \ \beta) \ \times \ 2 \ \times \ \sigma^2 \ / \ d^2$		How to cite this service	
where σ is the standard deviation, and		Sealed Envelope Ltd. 2012. Power calculator for continuous	
$f(\alpha, \beta) = [\Phi^{-1}(\alpha) + \Phi^{-1}(\beta)]^2$		outcome non-inferiority trial. [Online] Available from: https://www.sealedenvelope.com/power/continuous-noninferior/	
• ¹ is the cumulative distribution function of deviate.	a standardised normal	[Accessed Thu Jan 19 2023].	

The power calculation suggests 417 patients in each group, the expected drop-out rate of patients is 20% (results from the SR pilot study, Ferretti et al 2024), resulting in 500 patients per group.

7. Randomization and Blinding

Randomization Method

At screening, the order of diagnostic tests will be randomized. The "randomization system" (RS) will assign an unique identification number to the patient known as the patient number. This number will be associated with the patient throughout the study. Each patient signing an informed consent form (ICF) must be entered into the RS regardless of eligibility to obtain a patient number. This 8-digit number will consist of a 3-digit country specific code, followed by a 2-digit site identification and a 3-digit number assigned sequentially within each site to each patient, starting at 001.

At the randomization visit, all eligible patients will be randomly assigned in a 1:1 ratio to follow the routine clinical management or to be part of the SR clinical pathway. Centres using polysomnography as routine sleep evaluation procedure are asked to use this method in all of the study patients at this centre, and vice versa for those centers using cardiorespiratory polygraphy as the routine method. By this procedure, the study aims to recruit at least 40% of patients in the traditional clinical routine to be assessed by PSG. No formal stratification for anthropometric factors like age, BMI, gender or comorbidities will be performed.

Patients will be assigned a randomization number through the RS. Once a randomization number is allocated to one patient, it may not be assigned to another patient even if the former discontinued the study. The randomisation list is exemplified in appendix B.

Blinding

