8.1. General Considerations

The primary study outcome variable (staff time) will be analysed using an intent-to-treat (ITT) as well as a per-protocol analysis. Similarly, secondary and tertiary/exploratory outcome variables will be performed in the per protocol analysis cohort.

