8.4. Primary Analysis

Primary outcome: Staff time– comparison between standard care and the Sleep Revolution model in patients with suspected obstructive sleep apnea (OSA).

• Primary Outcome

The primary outcome is staff time, spent for the sleep apnea diagnostic pathway (V1a to V1 c) measured in minutes, required per patient, for the randomized study procedure (SC or SR care).

• Study Design

This is a parallel-group design comparing two patient groups (Group A and Group B). Patients are nested within centers, and the analysis will account for potential clustering by center. This is a non-inferiority comparison in staff time.

• Analysis Population

The primary analysis will be conducted on the intention-to-treat (ITT) population, including all randomized patients according to their assigned group.

• Descriptive Statistics

Descriptive statistics will be presented for staff time by group, including:

- Mean (standard deviation), Median (interquartile range), and Minimum/Maximum

• Primary Analysis

To compare staff time between the two groups while adjusting for center effects, a linear mixedeffects model (LMM) will be used:

- Fixed effect: Group (Group A vs. Group B)
- Random effect: Center (to account for clustering)
- Model specification:

StaffTime_{ij} = $\beta_0 + \beta_1 * Group_{ij} + u_j + \varepsilon_{ij}$

where:

- StaffTime_{ij} is the staff time for patient i in center j
- β_0 is the intercept
- β_1 is the fixed effect of group
- u_j ~ N(0, σ_u^2) is the random effect for center
- $\varepsilon_{ij} \sim N(0, \sigma^2)$ is the residual error

Adjustment for potential confounders would be considered if groups are unbalanced for some covariate due to random.

• Estimates and Inference

The estimated mean difference in staff time between groups will be reported with 95% confidence intervals and p-values.

Model assumptions (normality of residuals, homoscedasticity) will be checked using diagnostic plots.

Sensitivity Analyses

A per-protocol analysis will be conducted to assess robustness.

If the distribution of staff time is highly skewed, a log-transformation or non-parametric methods may be considered.

Two additional sensitivity analyses will be performed based on patient characteristics like A) sex and B) by the median of the age (total patient population).

Further sensitivity analysis will be performed regarding subgroups of centers and patient characteristics for sleep test methodology in the standard care arm:

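### The only per-protocol set in SAP 8.3 is labelled inconsistently and, read literally, requires both pathways, so it can drop valid staff times for the randomised pathway

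*SAP*

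**What the plan says.** SAP 8.3 gives one per-protocol definition. Its heading reads "Per protocol analysis population (PPAP) for the primary outcome", while the sentence beneath reads "All patients finally fulfilling the complete diagnostic pathway (SR och traditional) will constitute the per protocol analysis population for secondary and tertiary outcome analyses". No other criterion is listed.

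SAP 8.1 states that staff time "will be analysed using an intent-to-treat (ITT) as well as a per-protocol analysis". SAP 8.4 makes ITT the primary analysis and adds, under sensitivity analyses, "A per-protocol analysis will be conducted to assess robustness". The outcome itself is staff minutes "required per patient, for the randomized study procedure (SC or SR care)". Section 3 (Trial Design, Randomisation) explains that allocation fixes the first procedure, but that "each patient will also be studied with the respective other diagnostic arm (SC or SR)".

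**The concern.** There are two faults in one short definition.

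First, the heading and the sentence disagree on which outcome the set serves. If the sentence governs, the per-protocol analysis of staff time required by 8.1 and 8.4 has no population. If the heading governs, it has the wrong one.

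Second, the completion rule does not match the endpoint. Staff time belongs to the randomised pathway, and completing the other pathway is no part of it. A literal reading removes a patient whose randomised-pathway time is complete because a different procedure was not finished. What remains to be done also differs by arm. A patient randomised to standard care still faces three self-applied nights with the app and watch. A patient randomised to SR still faces the local routine test. Failure to finish can therefore be unequal between arms and related to patient characteristics.

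In a non-inferiority comparison the per-protocol analysis is read next to ITT as a check on the conclusion. A set selected on an event outside the endpoint makes that check harder to interpret.

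**Working it through.** **Passages side by side (all SAP)**

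| Item | Where | Content |
|---|---|---|
| Outcome served, per heading | 8.3 | Primary |
| Outcome served, per sentence | 8.3 | Secondary and tertiary |
| Completion required | 8.3 | SR 'och' traditional, literally both |
| Staff time measured for | 8.4 | The randomised procedure, SC or SR |
| Per-protocol analysis of staff time | 8.1, 8.4 | Required |
| Any other per-protocol set | whole SAP | None |

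The two-pathway reading is the plain meaning of 'och' and fits a design in which every patient undergoes both procedures. The Appendix A time sheet has separate blocks and sums for the SR and standard care procedures, plus an entry for the consultation. Completeness of the randomised pathway can therefore be judged without the other one.

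**The plan's own figure.** Inputs from section 6: one-sided alpha 1%, power 90%, SD 120, margin 30, true difference 0.

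n per group = (z₀.₉₉ + z₀.₉₀)² × 2 × SD² / d² = (2.326 + 1.282)² × 2 × 120² / 30² = 13.02 × 32 = 416.5, rounded up to 417 (834 in total). This reproduces exactly. The stated 500 per group follows as 417 × 1.2 = 500.4.

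**Effect of the rule on per-protocol power.** The SAP gives no rate of loss between the pathways, so the loss is an assumption, shown as a range. Starting from 500 supposes no other losses, which isolates the effect of the second-pathway criterion.

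Power = Φ( 30 / (120 × √(2/n)) − 2.326 )

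| Assumed loss at second pathway | n per group | Power, one-sided 1% |
|---|---|---|
| 0% | 500 | 94.8% |
| 5% | 475 | 93.7% |
| 10% | 450 | 92.3% |
| 20% | 400 | 88.7% |
| 30% | 350 | 83.7% |

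Worked line for n = 400: √(2/400) = 0.0707; 30 / (120 × 0.0707) = 3.536; 3.536 − 2.326 = 1.209; Φ = 0.887.

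Section 8.4 reports a 95% interval, which corresponds to one-sided 2.5%. With 1.960 in place of 2.326, power is 97.7% at 500, 97.1% at 475 and 91.1% at 350.

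The selection effect cannot be quantified. The SAP gives no completion rates by arm and nothing that relates non-completion to staff minutes, so neither its size nor its direction can be derived.

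**The case against.** The strongest reply is that this is a wording slip with little consequence. 'Och' is an untranslated word after a singular 'pathway', and 8.4 itself speaks of SC or SR care. If 'or' was meant, no valid time is dropped. ITT is expressly primary, completers of both procedures are a recognisable if narrow per-protocol set, and the loss of power is modest. Most of this stands as a limit on size. It does not remove the point: the text says 'and', the heading contradicts the sentence, and even the 'or' reading needs the text corrected.

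Three stronger inferences are tempting, and the documents do not support them.

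- *That patients are excluded for something that happened after their endpoint was complete.* Appendix A counts the patient's consultation with the doctor as staff time. The Blinding text in section 7 places the final diagnosis at the end of the diagnostic process, with the second package's results withheld at that point. The consultation may therefore follow both tests, and someone lost during the second pathway may lack a complete staff time. The order cannot be settled from the text, so no count of valid times lost can be given.
- *That the set knowingly keeps protocol violators.* No violation rate is given, only eligible patients are to be randomised, and deviation criteria may sit in the protocol. On the standard care test the wording is a request: "Centres using polysomnography as routine sleep evaluation procedure are asked to use this method in all of the study patients at this centre". Departing from it is not clearly a violation.
- *That the set should exclude standard care patients tested by another method.* This would be a post-randomisation exclusion in one arm only, with no SR counterpart. Section 8.4 already plans sensitivity analyses by polygraphy versus polysomnography and by home versus in-lab testing.

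**Conclusion.** The point holds as a defect in the definition of the per-protocol set. The heading and sentence of 8.3 conflict. Followed literally, the sole criterion can exclude complete randomised-pathway staff times from the robustness analysis because another pathway was not completed, and this selection may differ by arm.

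The size is moderate at most. Over the assumed 5% to 30% range the power cost is about 1 to 11 percentage points (94.8% to 93.7% or 83.7%). Possible selection matters more but cannot be measured from the SAP. The conclusion rests on reading 'och' as 'and', and on at least some patients having a complete randomised-pathway time, consultation included, without completing the other pathway.

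A reader might infer that the trial's main result is at risk. It is not: the primary estimate comes from the ITT population, and only the supporting per-protocol analysis is affected.

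**What to change.** Reword 8.3 before the analysis is run:

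1. Define a per-protocol set for staff time: eligible randomised patients who completed their randomised pathway, including the consultation, with a complete time sheet, whether or not they completed the other pathway.
2. Define a separate set of patients who completed both pathways, and use it for the paired SR–SC comparisons.
3. Make the heading and the sentence agree on which outcome each set serves, replace 'och', and state which pathway or pathways must be complete.
4. Do not add an exclusion on test method in the standard care arm. Leave that question to the sensitivity analyses by test type in 8.4.

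The cost is a few lines of SAP text and one derived flag. The time sheet in Appendix A already records the two pathways separately, so no new data are needed.

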8.4. Primary Analysis

Primary outcome: Staff time– comparison between standard care and the Sleep Revolution model in patients with suspected obstructive sleep apnea (OSA).

• Primary Outcome

The primary outcome is staff time, spent for the sleep apnea diagnostic pathway (V1a to V1 c) measured in minutes, required per patient, for the randomized study procedure (SC or SR care).

• Study Design

This is a parallel-group design comparing two patient groups (Group A and Group B). Patients are nested within centers, and the analysis will account for potential clustering by center. This is a non-inferiority comparison in staff time.

• Analysis Population

The primary analysis will be conducted on the intention-to-treat (ITT) population, including all randomized patients according to their assigned group.

• Descriptive Statistics

Descriptive statistics will be presented for staff time by group, including:

- Mean (standard deviation), Median (interquartile range), and Minimum/Maximum

• Primary Analysis

To compare staff time between the two groups while adjusting for center effects, a linear mixedeffects model (LMM) will be used:

- Fixed effect: Group (Group A vs. Group B)
- Random effect: Center (to account for clustering)
- Model specification:

StaffTime_{ij} = $\beta_0 + \beta_1 * Group_{ij} + u_j + \varepsilon_{ij}$

where:

- StaffTime_{ij} is the staff time for patient i in center j
- β_0 is the intercept
- β_1 is the fixed effect of group
- u_j ~ N(0, σ_u^2) is the random effect for center
- $\varepsilon_{ij} \sim N(0, \sigma^2)$ is the residual error

Adjustment for potential confounders would be considered if groups are unbalanced for some covariate due to random.

• Estimates and Inference

The estimated mean difference in staff time between groups will be reported with 95% confidence intervals and p-values.

Model assumptions (normality of residuals, homoscedasticity) will be checked using diagnostic plots.

Sensitivity Analyses

A per-protocol analysis will be conducted to assess robustness.

If the distribution of staff time is highly skewed, a log-transformation or non-parametric methods may be considered.

Two additional sensitivity analyses will be performed based on patient characteristics like A) sex and B) by the median of the age (total patient population).

Further sensitivity analysis will be performed regarding subgroups of centers and patient characteristics for sleep test methodology in the standard care arm:

- polygraphy versus polysomnography,
- home versus in lab sleep evaluation,
- manual versus automatic sleep evaluation,
- and subclassification of staff time (Technician/nurse time for patient meeting, sleep analysis, physicians time with the patient.)

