All innovation in medicine needs to be justified in terms of cost-benefit. We decided to use stafftime as the primary outcome of the current study. It is estimated that the time of the SR procedure is equal to the time presently used in the SC procedures. Use of the self-applied polysomnography together with machine-learning algorithms of sleep analysis and the digital platform of patient symptom self-reporting will reduce staff time on one hand. On the other hand, user instructions to the patient for the different technologies as well as the evaluation of new information may consume more time compared with the current procedure. We decided to use a non-inferiority study design with 30 minutes as a threshold for equality of staff time within the setting of 24 sleep centers in Europe.

Calculation of the power sample is based on a previous publication (Fischer 2008) and the following assumptions determined from a Delphi round (expert consensus) amongst the participating study centers. More detailed information on staff time for PSG and HSAT currently used at 24 different study sites are not available in the literature. One pilot study for the SR pathway has been performed but no detailed measurement of staff time was performed. However, realistic estimates can be made (see table below).

Work modules	Standard PSG	Standard HSAT	Sleep Revolution	Value
Preparation technical pre/post	15	10	35	
Instructions/Hook up	20-40	5-20	5-30	
Performance of the sleep test	120-480	0 (patient)	0 (patient)	
Evaluation of the sleep test	30-120	5-30	30-90	
Questionnaires	5	5	10	
Additional equipment	0	0	15	
Doctor: interpretation, communication	30-60	15-30	45-60	
Staff time: Estimated range of the mean	220-720	40-95	140-240	
Staff time: Estimated standard deviation of the mean	180	30	60	120

Power calculation:

Significance level (alpha)	1%		
Power (1-beta)	90%	You could say:	
Standard deviation of outcome	120	between the standard and experimental treatment, then 834	
Non-inferiority limit, d	30	sure that the lower limit of a one- sided 99% confidence interval (or equivalently a 98% two-sided	
Sample size required per group	417	confidence interval) will be above the non-inferiority limit of -30.	
Total sample size required	834		
Technical note		Reference	
Calculation based on the formula:		Julious SA. Sample sizes for clinical trials with Normal data. Statis Med. 2004; 23:1921-1986.	

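### The primary model fits one common staff-time difference and one residual variance, although the plan's own table puts SR outside the 30-minute margin against HSAT and inside it against attended PSG

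*SAP*

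**What the plan says.** SAP Section 8.4 models staff time as an intercept, a single group effect, a centre term ("Random effect: Center (to account for clustering") and one residual variance. It has no term for the standard-care method and no group-by-method term.

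Section 6 sets a "non-inferiority study design with 30 minutes as a threshold for equality of staff time". It sizes the trial with one common "Standard deviation of outcome" of 120 min, a true difference of zero, and a one-"sided 99% confidence interval (or equivalently a 98% two-sided" interval. The table above that calculation, repeated in Appendix A, has a row "Staff time: Estimated range of the mean": 220–720 min for PSG, 40–95 for HSAT and 140–240 for SR. The SDs beneath it are 180, 30 and 60.

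Section 7 asks each centre to keep to its routine method, PSG or polygraphy, for all its study patients, and says that "the study aims to recruit at least 40% of patients in the traditional clinical routine to be assessed by PSG". No upper limit is given.

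The method appears elsewhere in three places:
- Section 8.4 lists "polygraphy versus polysomnography" among the sensitivity analyses of the primary outcome, separately from home versus in-lab testing.
- Section 8.7 repeats the split for secondary and exploratory analyses and counts AASM levels 1 and 2 together as PSG.
- Section 11 allows robust standard errors or weighted least squares if unequal variance is found.

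On covariates, Section 8.4 says: "Adjustment for potential confounders would be considered if groups are unbalanced for some covariate due to random".

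**The concern.** The comparator is fixed by centre and is not one thing. If the table is near the truth, the SR-minus-SC difference has opposite signs in PSG and HSAT centres, and the two fall on opposite sides of the margin. A single group coefficient then estimates a weighted average whose weights are the recruitment shares, and the plan does not state those weights as part of what is estimated.

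Two things are at stake. A pooled pass could be taken as no excess staff time by HSAT centres, where the plan's own figures imply an excess beyond the margin. And the model puts the method difference into the residual, so the confidence interval used for the verdict has the wrong width.

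**Working it through.** **Plan's own figures.** n = (2.326 + 1.282)² × 2 × 120² / 30² = 13.02 × 32 = 416.5, so 417 per group, as stated. The table's range row also adds up:
- PSG: 15+20+120+30+5+0+30 = 220, to 15+40+480+120+5+0+60 = 720
- HSAT: 10+5+0+5+5+0+15 = 40, to 10+20+0+30+5+0+30 = 95
- SR: 35+5+0+30+10+15+45 = 140, to 35+30+0+90+10+15+60 = 240

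**Difference by method, over the whole ranges.**
- SR − HSAT is at least 140 − 95 = +45 min, above 30 for every pair of values.
- SR − PSG is at most 240 − 220 = +20 min, below 30 for every pair of values, with the test attended as tabulated.

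**Pooled difference at PSG share p** = p × (SR − PSG) + (1 − p) × (SR − HSAT).

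| Means used (PSG, HSAT, SR) | SR − PSG | SR − HSAT | Pooled at p = 0.40 | Share where pooled = 30 |
|---|---|---|---|---|
| Midpoints (470, 67.5, 190) | −280 | +122.5 | −112 + 73.5 = −38.5 | 92.5/402.5 = 23% |
| All low ends (220, 40, 140) | −80 | +100 | −32 + 60 = +28 | 70/180 = 39% |
| All high ends (720, 95, 240) | −480 | +145 | −192 + 87 = −105 | 115/625 = 18% |

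**Standard error for these 24 centres, mix held fixed.** Assumptions: 10 PSG and 14 HSAT centres, 17 patients per arm per centre (816 in all), and the table SDs taken as patient-level SDs.
- Mean within-cell variance: [10 × (180² + 60²)/2 + 14 × (30² + 60²)/2] / 24 = (180,000 + 31,500)/24 = 8,812.5.
- True SE of the pooled difference: √(8,812.5 × 4/816) = 6.6 min, whatever the means.
- The omitted interaction adds p(1 − p) × gap²/4 to the residual variance, with p = 10/24. At midpoints this is 0.243 × 402.5²/4 = 9,844; at the low ends 0.243 × 180²/4 = 1,969.
- Model SE at midpoints: √(18,656.6 × 4/816) = 9.6 min. At the low ends: √(10,781 × 4/816) = 7.3 min.

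Simulation agrees: 9.7 against 6.3 at midpoints and 7.3 against 6.7 at the low ends.

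**Does the mix decide the verdict?** At the low ends, simulated pass rates (upper limit of the 98% two-sided interval below 30) are 2%, 62% and 99% with 10, 12 and 14 PSG centres, that is shares of 42%, 50% and 58%. A hand check for 12 centres: true difference +10, model SE 7.7, true SE 7.0, so Φ[(30 − 2.326 × 7.7 − 10)/7.0] is about 0.61. With the 95% interval that Section 8.4 reports, the simulated rates are 9%, 77% and 100%. At midpoints, 10 or more PSG centres pass every time.

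**Why the variance must differ by arm and method.** In a balanced design the common variance does no harm to the pooled SE; the interaction is the whole excess. It does harm the method-specific intervals. With 170 and 238 patients per arm, a common variance gives SEs of √(17,625/170) = 10.2 (PSG) and √(17,625/238) = 8.6 (HSAT). The correct values are √(36,000/170) = 14.6 and √(4,500/238) = 4.3.

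**The case against.** A contrast with each centre's usual care is a legitimate pragmatic question, and Section 8.4 already plans the polygraphy/PSG, home/lab and scoring splits for the primary outcome. That stands, and it is why the pooled test need not be abandoned. But a sensitivity split leaves the primary model and its interval as they are. Covariate adjustment triggered by chance imbalance does not address a difference in effect between methods.

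Four stronger readings are tempting, and the document does not support them.
- **That the verdict always depends on the mix.** At table midpoints every share at or above the 40% aim passes. The mix decides within the planned range only if the true means lie towards the low PSG or high SR end.
- **That the error bars are far too narrow.** For these centres with their mix fixed they are too wide, which is conservative. A much larger SE arises only if centres are redrawn so that the PSG count varies: 402.5 × √(0.24/24) = 40 min at midpoints. Section 6 sets the margin within the 24 participating centres, and Section 13 lists centre heterogeneity and limited generalisability as limitations, so the plan does not clearly claim that wider target.
- **That SR is inside the margin against all PSG.** The +20 bound includes 120–480 min of attendance. If unattended level 2 PSG is used and that row is zero (an assumption), the column sums to 100–240 and SR − PSG runs from −100 to +140.
- **That the pooled test must give way to two separate verdicts.** This would change the question, reduce precision in each stratum, and need a rule for conflicting results.

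**Conclusion.** The point holds as a fault in the primary model. The plan's own table implies differences of at least +45 min (HSAT) and at most +20 min (attended PSG) around a 30-min margin, yet the model allows one difference and one variance. The pooled result is an average with unstated weights. It is robust to the mix at midpoints (−38.5 min at 40% PSG) and not at the low ends (+28 min at 40%).

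The model SE for these centres is about 45% too wide at midpoints (9.6/6.6) and about 10% too wide at the low ends (7.3/6.6). This costs power and does not inflate false claims of non-inferiority. The SE would be too narrow only for inference to a wider population of centres.

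The method contrast rests only on the table's ranges and on PSG being attended. The SE figures also assume equal centre sizes, balanced arms within centres and table SDs that describe patients; the table labels them as SDs of the mean.

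**What to change.** In Section 8.4:
- Add standard-care method to the fixed effects, separating attended from unattended PSG if both are used, and add group by method. Let the residual variance differ by arm and method. Keep the random centre intercept.
- Keep the pooled non-inferiority test, defined as the group difference standardised to the actual method mix, and state that mix.
- Beside it, report each method-specific difference with its confidence interval against the 30-min margin, and say that a pooled pass does not establish non-inferiority in HSAT centres.
- Use a random group slope by centre only as a sensitivity analysis for generalising beyond these centres. As the sole pooled test without a method term, its SE would be about √(40² + 6.6²) = 41 min at midpoints or √(18² + 6.6²) = 19 min at the low ends, with power at a true difference of zero of about 6% or 22%.

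The variances should not be freed without the interaction. Inverse-variance weighting, which the weighted least squares option in Section 11 could bring in, would pull the common difference towards HSAT centres. With centre-level variances of 36,000/17 = 2,118 (PSG) and 4,500/17 = 265 (HSAT), the 10 PSG centres carry (10/2,118) / (10/2,118 + 14/265) = 8% of the weight. The midpoint estimate then moves from about −45 min to 0.08 × (−280) + 0.92 × 122.5, about +90 min.

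The cost is SAP wording and modest programming through the amendment route in Section 14. The downside is slightly more modelling, and HSAT centres will probably be shown to exceed the margin.
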